#### 7.6. Treatment of Overdose

No specific information is available on the treatment of overdose of pembrolizumab or IFX-1. For this study, an overdose of pembrolizumab will be defined as any dose of  $\geq$ 1000 mg. In the event of overdose, the participant should be observed closely for signs of toxicity. Appropriate supportive treatment should be provided if clinically indicated.

In the event of an overdose, the investigator should:

- 1. Contact the medical monitor immediately
- 2. Closely monitor the patient for any AE/SAE and laboratory abnormalities
- 3. Report the overdose (IFX-1 only symptomatic, pembrolizumab symptomatic and asymptomatic overdoses) in accordance with the Section 9.2 through the SAE page in the eCRF. Document the actually delivered dose of the IMP as well as the duration of infusion in the eCRF SAE page (narrative section) within **24 hours** of event occurrence.
- 4. In addition, document the actual dose added to the infusion bag, the duration of the infusion, and the actually delivered dose on the respective IMP administration pages in the eCRF.

Decisions regarding dose interruptions or modifications will be made by the investigator in consultation with the medical monitor based on the clinical evaluation of the patient.

#### 8. STUDY ASSESSMENTS AND PROCEDURES

Patient consent will be obtained prior to performance of any study related procedures; standard of care procedures applicable to screening obtained within 28 days of first drug administration (or

clearly medically relevant for this period, as agreed by the sponsor,) can be used for qualification unless otherwise specified.

Study procedures and their timing are summarized in the SoA (Table 1) and further detailed per study period and visit in Appendix 1.

Details on the assessments and procedures are given in the following subsections.

Safety concerns should be discussed with the sponsor immediately upon occurrence or awareness to determine if the patient should continue or discontinue any study treatment.

Adherence to the study design requirements, including those specified in the SoA (Table 1), is essential and required for study conduct.

All screening evaluations must be completed and reviewed to confirm that potential patients meet all eligibility criteria (Sections 6.1 and 6.2). An eligibility form will be used to enable the sponsor to agree on inclusion and assignment to a treatment arm. The investigator will maintain a screening log to record details of all patients screened and to confirm eligibility or record reasons for screening failure, as applicable.

For details on the amount of blood collected from each patient over the duration of the study, see Laboratory Manual.

# **8.1.** Baseline Assessments

The following procedures will be performed to assess baseline characteristics during screening evaluations and before study treatment administration:

- Documentation of demographic details (age, gender, race, and ethnicity), medical and disease history (see Sections 8.1.1 and 8.1.2)
- Disease assessments (see Section 8.2 and Appendix 3)
- QoL/EORTC (see Section 8.8)
- Documentation of concomitant disease and prior and concomitant medications (see Sections 8.1.3 and 8.1.4)
- Baseline safety assessment (height, weight, physical exam, vital signs, electrocardiogram (ECG), AEs, and safety laboratory; see Section 8.3)
- Skin or metastasis biopsy (if skin biopsy is not possible) for biomarker assessments (see Section 8.6)
- Baseline assessment of pharmacodynamic parameters (C3a, C5a, ADA) and PK

# 8.1.1. Medical History (Except cSCC History)

The documentation of the patient's medical history includes any details on the patient's medical history before enrollment into the study. The information must be documented as such in the source documentation and eCRF.

# 8.1.2. cSCC (Disease) History

Any details on the patient's cSCC disease history including any cSCC therapy (surgery, systemic therapy, radiation therapy by verbatim name with start and end dates, dosages) that the patient received will be documented in the source documentation and in the eCRF.

#### 8.1.3. Concomitant Disease

All ongoing diseases diagnosed prior to enrollment into the study are regarded as concomitant diseases. All concomitant diseases must be documented in the patient file and in the eCRF.

# 8.1.4. Prior and Concomitant Medication/Treatments

All prior anticancer medication irrespective of the time of treatment and any medication or vaccine (including over the counter or prescription medicines, vitamins, and/or herbal supplements) that the patient is receiving within 28 days prior to the first dose of study treatment and up to 30 days after the last dose should be recorded in the patient file and in the eCRF along with:

- Reason for use
- Dates of administration including start and end dates
- Dosage information including dose, route and frequency

The medical monitor should be contacted if there are any questions regarding concomitant or prior therapy.

In case of SAEs occurring later than 30 days after the last dose of study treatment, respective concomitant medications administered should be recorded.

# 8.2. Efficacy Assessments

Tumor assessments and response evaluation will be done per modified RECIST v1.1 (Eisenhauer et al., 2009) followed by iRECIST. iRECIST introduces additional tumor assessment and response evaluation criteria at time of a first response evaluation of PD according to RECIST v1.1, to accommodate for situations where a pseudo-progression is suspected (Seymore et al., 2017). Tumor assessments, using adequate imaging techniques including standardized medical photography, and response evaluation will be performed and documented after every cycle throughout the study. In case patients experience a PR/iPR or CR/iCR that lasts ≥1 year, imaging frequency can be decreased to every other cycle. For further details see Appendix 3. Independent

response evaluation could be initiated by the sponsor any time during the study. In preparation of a conditional, result-driven independent response evaluation, copies of all tumor assessment images will be collected.

# 8.2.1. Imaging Requirements

Medical photography and computed tomography (CT) or magnetic resonance imaging (MRI) for tumor assessment will be performed locally at each scheduled tumor assessment time point (after every cycle), and at any time when disease progression is suspected.

Note: after a response evaluation of PD/iCPD while on study treatment, additional scans are not required at scheduled follow-up visit procedures.

The choice of whether the imaging is by CT or MRI is an investigator decision (see Appendix 3). Once the choice has been made to use CT scan or MRI, subsequent assessments should be made using the same modality whenever possible.

# 8.2.2. Evaluation of Overall Response

The best overall response is the best response recorded from the start of the study treatment until EOT or documentation of disease progression according to RECIST v1.1/iRECIST (PD/iCPD). The patient's best overall response assignment will depend on the findings of both target and non-target disease, appearance and size of new lesions, and clinical stability (see Appendix 4). For patients discontinuing treatment for other reasons than PD/iCPD, the tumor assessments will continue during the follow-up period (also see the SoA, Table 1).

# **8.3.** Safety Assessments

Safety will be assessed based on the following variables:

- AEs (see Section 9 and Section 8.3.1)
- Laboratory safety parameters and pregnancy test (see Section 8.3.2)
- Vital signs (see Section 8.3.3)
- ECG (see Section 8.3.4)
- Physical examination, ECOG PS (see Section 8.3.5)
- Immunogenicity/IFX-1 ADA status (see Section 8.3.6)

Planned time points for all safety assessments are provided in the SoA (Table 1).

# **8.3.1.** Adverse Events Assessments

AEs will be assessed throughout the study from informed consent to EOS at each study visit. For details on AE collection and reporting, see Section 9. The investigator should take appropriate measures to follow all AEs until clinical recovery is complete and laboratory results have returned

to normal, or until progression has been stabilized, or until death, in order to ensure the safety of the patients. This may imply that observations will continue beyond the last planned visit per protocol, and that additional investigations may be requested by the sponsor. When study treatment is prematurely discontinued, the patient's observation will continue until the EOS for that patient.

# 8.3.2. Clinical Safety Laboratory Assessments

Blood samples for safety laboratory analysis should be obtained after the patients have provided responses to QoL questionnaire and after vital signs assessments have been performed, but before administration of study treatment.

See Appendix 2 for the list of clinical laboratory tests to be performed and the SoA (Table 1) for timing and frequency.

The investigator must review the laboratory report, document this review, and record any clinically relevant changes (clinically relevant abnormal findings) occurring during the study in the AE section of the eCRF. The laboratory reports must be filed in the patient file. Clinically relevant abnormal laboratory findings are those which are not associated with the underlying disease, unless judged by the investigator to be more severe than expected for the patient's condition.

All laboratory tests with values considered clinically relevantly abnormal occurring until 30 days after EOT should be reported in the AE section of the eCRF and repeated until the values return to normal or baseline, are no longer considered clinically relevant by the investigator or medical monitor, or until the EOS (also see Section 9 and Appendix 6).

If such values do not return to normal/baseline within a period of time judged reasonable by the investigator, the etiology should be identified, and the sponsor notified.

All protocol-required laboratory assessments, as defined in Appendix 2, must be conducted in accordance with the SoA (Table 1).

If laboratory values from non-protocol specified laboratory assessments performed at the institution's local laboratory require a change in patient management or are considered clinically relevant by the investigator (e.g., SAE or AE or dose modification), then the results must be recorded in the eCRF.

For details on pregnancy testing, refer to Appendix 7.

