# 9.5. Abnormal Laboratory Values/Vital Signs/Electrocardiogram/Physical Examination

Abnormalities of Laboratory results/vital signs/ECG/physical examination should be reported as AEs (using the NCI CTCAE v5.0 terminology) particularly if  $\geq 1$  of the following is met:

- Any criterion for an SAE is fulfilled
- The abnormality causes the patient to discontinue from the study treatment.
- The abnormality causes the patient to interrupt the study treatment or a modification of dosing.
- The abnormality requires intervention as corrective treatment or consultation.
- The investigator judges that the abnormality is clinically relevant and should be reported as an (S)AE in the eCRF.

All laboratory tests for which abnormal results are collected after the initiation of study treatment should be repeated until the values return to normal or to a stable status. All abnormal results are assessed as clinically relevant by the investigator must be reported as an AE. The frequency of such checks is at the investigator's discretion depending on the degree of abnormality. The reporting of laboratory/vital signs/ECG/physical examination abnormalities (e.g., anemia) as both AEs and a specific finding of laboratory values/vital signs/ECG (e.g., decrease in red blood cells) should be avoided.

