# **Appendix 6** Adverse Events: Definitions and Procedures

#### I. Definitions

#### **Definition of an AE**

An AE is any untoward medical occurrence in a patient or clinical study patient, temporally associated with the use of study treatment, whether or not considered related to study treatment.

NOTE: An AE can therefore be any unfavorable and unintended sign (including an abnormal laboratory finding), symptom, or disease (new or exacerbated) temporally associated with the use of study treatment.

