#### **Events Meeting the AE Definition**

- Any clinically significant laboratory test results (hematology, clinical chemistry, or urinalysis)
  or other safety assessments (e.g., ECG, radiological scans, vital signs measurements),
  including those that worsen from baseline. Laboratory tests are considered clinically
  significant, if:
  - Any criterion for an SAE is fulfilled
  - The abnormality causes the patient to discontinue from the study treatment
  - The abnormality causes the patient to interrupt the study treatment or a modification of dosing
  - The abnormality requires intervention as corrective treatment or consultation
  - The investigator judges that the abnormality is clinically relevant and should be reported as an (S)AE in the eCRF
- Exacerbation of a chronic or intermittent pre-existing condition including either an increase in frequency and/or severity of the condition
- New conditions detected or diagnosed after study treatment administration
- Signs, symptoms, or clinical sequelae of a suspected drug-drug interaction
- Signs, symptoms, or clinical sequelae of a suspected overdose of a study treatment constitute an SAE. Asymptomatic overdose must only be reported as an SAE if observed for pembrolizumab.
- Signs, symptoms, and/or clinical sequelae resulting from disease progression will be reported
  as AE or SAE if they fulfil the definition of an AE or SAE. The terms "disease progression",
  "progressive disease", or similar, per se will not be reported as an AE or SAE. Such instances
  will be captured in the efficacy assessments.

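### Sections 8.3.2 and 9.5 set different rules for recording a laboratory abnormality as an AE, and disease-attributed, no-worse-than-expected findings that are treated or interrupt dosing fall between them

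*Combined protocol and SAP*

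**What the plan says.** **Section 8.3.2 (clinical safety laboratory assessments).** The investigator must review each laboratory report and "record any clinically relevant changes (clinically relevant abnormal findings) occurring during the study in the AE section of the eCRF". The section then defines the term: "Clinically relevant abnormal laboratory findings are those which are not associated with the underlying disease", with an exception for findings the investigator judges more severe than the patient's condition would lead one to expect. The same section later adds the pointer "also see Section 9 and Appendix 6".

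**Section 9.5.** Abnormal results should be reported as AEs, particularly when at least one trigger is met. The triggers are an SAE criterion, discontinuation of study treatment, interruption or dose change ("The abnormality causes the patient to interrupt the study treatment or a modification of dosing"), treatment ("The abnormality requires intervention as corrective treatment or consultation"), or the investigator's judgement that the finding is relevant. None carries an exemption for disease-related findings.

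**Appendix 6, part I.** The same triggers define when a laboratory test is clinically significant and so an AE. An AE is any untoward occurrence "whether or not considered related to study treatment". The effects of progression are covered too: "Signs, symptoms, and/or clinical sequelae resulting from disease progression will be reported" as AEs or SAEs if they meet the definition. Only the bare term for progression is left out.

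**Endpoints and analysis.** Section 4.2.1.2 makes the frequency, severity and attribution of TEAEs and SAEs co-primary with best ORR in the Phase II portion of Arm B. Section 4.2.2.1 makes them secondary in Arm A. Section 10.3.2 defines a TEAE by its onset relative to first dosing, with no condition on cause.

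**The concern.** The endpoint counts events of any cause, but one of the recording rules that feed it screens on cause first. If a site applies the Section 8.3.2 definition, a finding it regards as part of the cancer and about as bad as expected never becomes an AE record, even when it was treated or led to a held dose. Relationship is assessed only for recorded AEs (Section 9.3 and Appendix 6, part II), so the screen acts before the step designed to deal with cause.

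That order matters because disease and drug are not exclusive explanations under the protocol's own scheme. In Section 9.3, a plausible origin in the patient's clinical state is one of the criteria listed for a possible relationship. A finding can therefore be disease-associated and still possibly related. The study is open-label and non-randomized, and eligibility admits AST and ALT up to 5 × ULN in patients with liver metastases, a setting in which the two causes are hard to separate.

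**Working it through.** The plan states no figure on this point, so the check is mainly a comparison of texts.

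**Step 1. Apply both rules to each kind of abnormality.**

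| Laboratory abnormality | Section 8.3.2 definition | Section 9.5 / Appendix 6 triggers | Agree? |
|---|---|---|---|
| Not attributed to disease; treated or dosing interrupted | Inside | Inside | Yes |
| Attributed to disease, worse than expected; treated or dosing interrupted | Inside, by the exception | Inside | Yes |
| Attributed to disease, no worse than expected; treated or dosing interrupted | Outside | Inside | **No** |
| Attributed to disease, no worse than expected; no consequence and not judged relevant | Outside | No trigger met | Yes |

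The third row is the gap. It follows from the full 8.3.2 condition, "not associated with the underlying disease, unless judged by the investigator to be more severe than expected for the patient's condition", set against triggers that do not ask about cause.

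**Step 2. Does the cross-reference settle it?** Section 8.3.2 refers to Section 9 and Appendix 6 without giving an order of precedence. Within Section 9.5, the trigger list is introduced by *should* and *particularly*. The sentence there that uses *must* applies to results the investigator assesses as clinically relevant, which is the very term that 8.3.2 defines with the disease condition. A reader who follows the pointer can carry the condition into Section 9.5. Appendix 6 uses a different term, *clinically significant*, for the same trigger list. Section 8.3.2 is also not uniform: for laboratory tests outside the protocol, its examples of relevance are an SAE, an AE or a dose modification, with no mention of disease.

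**Step 3. Does the gap reach the endpoint?** Yes. Under Section 10.3.2 an event in the third row with onset after first dosing would be a TEAE if recorded. It would enter the preferred-term counts and, at its maximum grade, the grade tables.

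**Step 4. Scale per affected patient.** Inputs: 29 patients per arm in the Phase II analyses, and up to 41 patients planned in Arm B (both Section 10.1). For *k* patients whose only event of a given type is recorded under one rule and not the other, the shift in that event's frequency is 100 × *k* / *n* percentage points.

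- *n* = 29: 1/29 = 3.4; 2/29 = 6.9; 3/29 = 10.3.
- *n* = 41: 1/41 = 2.4; 2/41 = 4.9; 3/41 = 7.3.

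The documents give no rate for *k*, so the actual shift cannot be computed. Its direction can be stated: the 8.3.2 condition only removes events, so any distortion lowers the count.

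**The case against.** The best defence is that the rules add to one another. Section 8.3.1 sends the reader to Section 9 for AE collection and reporting, Section 8.3 lists 8.3.2 only for laboratory parameters, and 8.3.2 itself points to Section 9 and Appendix 6. Nothing in 8.3.2 forbids reporting other abnormalities. On that reading every finding that meets a Section 9.5 trigger is an AE and nothing is lost. This has real weight: a reader might infer a flat contradiction, and the documents do not support that. They contain two unreconciled definitions. The additive reading is available but not stated, and the shared term in Section 9.5's mandatory sentence leaves it open to doubt.

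A reader might also infer that any abnormality blamed on the tumour escapes AE recording under 8.3.2. It does not. The exception brings back whatever is judged worse than expected, and higher-grade findings are the likeliest to qualify or to meet an SAE criterion.

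Nor do the documents support a claim that the main liver signals would be missed. Appendix 2 requires ALT ≥3 × ULN with bilirubin ≥2 × ULN to be reported as an SAE. Section 9.7.2 makes a combined transaminase and bilirubin rise, with alkaline phosphatase below 2 × ULN, an AESI for pembrolizumab, and Section 9.7 requires AESIs to be reported whatever their relationship. Isolated transaminase rises are not covered by these rules.

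Finally, the safety co-primary is descriptive, with no test or threshold; inference rests on ORR. Laboratory values are summarised by visit, with shift tables to the worst value where applicable, so an unrecorded AE would still show in the laboratory data. All of this stands. It limits the consequence without closing the gap.

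**Conclusion.** Wrong as written: the recording rules conflict for a narrow but identifiable group, namely laboratory abnormalities attributed to the disease and no worse than expected that are treated or interrupt dosing. For that group an all-cause TEAE can be dropped before its relationship to treatment is assessed, and laboratory preferred-term and grade counts can be understated. Each affected patient moves a given event frequency by 3.4 points with 29 patients, or 2.4 with 41. This assumes that at least some sites apply the 8.3.2 definition on its own and that the patient has no other event of the same type.

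Stronger conclusions are not supported. A reader might assume that 10% to 30% of patients have such an event and infer 29 × 0.10 = 2.9 to 29 × 0.30 = 8.7 patients per arm. No such rate is in the documents, and the figure would be a ceiling: every event would have to be judged no worse than expected and every site would have to follow 8.3.2 alone. The overall proportion of patients with any TEAE need not move, since a patient with another TEAE still counts. Variation between sites is possible but not shown. Laboratory summaries, shift tables and the combined ALT/bilirubin reporting rules are unaffected.

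**What to change.** In Section 8.3.2, replace the definition that rests on association with the underlying disease by a sentence such as: *A laboratory abnormality that meets any criterion in Section 9.5 is recorded as an AE whatever its presumed cause; a disease cause is entered through the relationship assessment (Section 9.3).* Bring the eCRF completion guidelines into line.

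The cost is one sentence and a guideline update. The downside is more AE records and a slightly higher reported TEAE rate. The change concerns AE recording only and alters nothing in dosing or patient management.

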#### 8.3.3. Vital Signs

Core body temperature, heart rate, respiratory rate, and blood pressure (diastolic and systolic) will be assessed at each visit at pre-dose, and H0+1h (±5 minutes), where H0 is the beginning of IFX-1 administration, on the days of study treatment administration and at further time points whenever medically indicated.

Blood pressure and pulse measurements will be assessed with a completely automated device. Manual techniques will be used only if an automated device is not available.

Vital signs will be measured in a semi-supine position after 5 minutes rest and will include temperature, systolic and diastolic blood pressure, and pulse and respiratory rate.

